5.2. Recruitment

5.2.1 Recruitment at sites

Participants will be recruited via clinic visits. The site team may review clinic lists for upcoming appointments to identify potentially eligible participants and contact these participants with an email link to the trial website where more information will be displayed and they will have the choice to sign up to receive the Patient Information Sheet (PIS) and commence pre-screening. Once enrolment is confirmed the participant will attend their clinic appointment as planned. Participants may also be approached at ongoing clinic visits and given the PIS. Flyers and posters will also advertise the trial in clinic waiting rooms. Participants who are recruited and consent in this way will be immediately enrolled and screened at their ongoing clinic visit.

5.2.2 Central recruitment

Participants will primarily be recruited via social media with central recruitment conducted by the Lindus Health team. Advertising on Facebook and other platforms will be used to highlight the trial to individuals who may be looking for screening. Adverts will make clear that the trial does not replace the need to seek medical advice. Adverts will direct potential participants to the trial website, where more information about the trial will be displayed and have the choice to sign up to receive the PIS. Once enrolled participants will book an in person clinic appointment to see a trial nurse at a clinic.

5.2.2 Participant Payments

All participants will receive £50 (UK) or €60 (Italy) for taking part in the trial on completion of all trial activities.

5.3. Pre-screening

Potential participants recruited centrally via social media, or sent information by the recruiting site in advance of a clinic visit, will be directed to the trial webpage, where they will be informed about the trial. If interested in taking part, they will complete an online pre-screening form to assess their eligibility for the trial.

If potentially eligible and once they submit the form, the PIS and Informed Consent Form (ICF) will be sent directly to the participant.

5.4. Informed Consent

Prior to consent, the potential participant will have received the PIS and ICF describing the trial. They will have had the opportunity to read through the details relating to the exact nature of the trial, the known side-effects and any risks involved in taking part. It will be clearly stated that the participant is free to withdraw from the trial at any time for any reason without prejudice to future care, without affecting their legal rights, and with no obligation to give the reason for withdrawal. It will be confirmed that potential participants have reviewed the PIS.

Adequate time will be given to the participant to consider the information and to ask any questions about the trial before deciding whether to participate. A trial team member experienced and trained in the informed consent process, will be available in person (in Italy) or via telephone (in Italy and the UK), prior to enrolment, if the participant has any questions regarding the trial. If the participant is willing, informed consent will be obtained.

The participant will provide their electronic signature at the end of the e-consent form and the central trial team member will verify the consent form. A copy of the ICF will be sent to the participant by email and an electronic copy retained by Lindus Health in a secure area with restricted access. In the case of paper consent signed in person, a copy of the completed consent form will be given to the participant and the signed consent form will be stored in a secure area with restricted access. In the UK, the participant's GP will be informed of their involvement in the trial.

Once the ICF has been signed the participant will complete the screening and eligibility assessment online or will complete screening and eligibility with the trial team at the clinic.

5.5. Screening and Eligibility Assessment

5.5.1. Screening and Eligibility Completed Centrally

Screening and eligibility will be self-reported via a survey on the trial website. Participants in group 1 will be asked to upload evidence of their recent HPV diagnosis (e.g. via a screenshot of their medical record in the NHS app). Eligibility data will be reviewed by the central trial team or site staff to confirm enrollment into the trial.

5.5.2. Screening and Eligibility at Sites

[figure not shown]
In cases where participants are identified via clinics lists in advance pre-screening and screening and eligibility will be completed online (see section 5.3 and 5.5.1). Where participants are recruited at clinic visits screening will be completed by a site staff member at that clinic visit. Eligibility will be reviewed and confirmed by the site team for enrolment into the trial.

5.5.3. Screen Failures

A screen failure is defined as a participant who consents to participate in the trial but is not subsequently assigned to the trial group. Minimal information, including Electronic Informed Consent Form (eIC) details, eligibility criteria, and demographics, will be collected. Individuals who do not meet the criteria for participation in this trial (screen failure) will not be rescreened.

5.6. Registration / Enrolment & Randomisation

Once eligibility has been confirmed by the site team participants will be enrolled and randomised to a sampling order using a block randomisation method. Participants in group 1 will be stratified by country. Randomisation will be performed at the point of enrolment by a member of the trial team using a pre-generated list of treatment allocation blocks.

Participants will be assigned a trial number in the format STP-[UK/IT]-NUMBER.

5.7. Baseline Data

Participants will be asked to provide demographic data and information on their medical history following their enrollment into the trial. Participants recruited centrally

will be asked to book a clinic appointment. Participants recruited at sites will be provided with clinic appointment(s) by the site trial team.

5.8. Blinding and code-breaking

There will be no blinding in this trial.

5.9. Tampon Sampling & Self-Swab

Following enrolment and provision of baseline data participants will be provided with a trial kit (via post) containing the Daye Diagnostic Tampon (DDT) and the self-swab. An instruction booklet and sterile containers for each sample will also be provided. Participants will perform sampling in an order according to a randomisation which will place them in Group A (self-swab then DDT) or Group B (DDT then self-swab). The instructions provided to the participant in the trial kit will provide them with the sample order. A gap of at least 1 hour should be left between the samples in both groups.

5.10. Trial Clinic Visit

All participants will attend at least one clinic visit as part of their participation in the trial. During this visit the following assessments will be performed:

- Participants will meet with a trial nurse who will take a clinician administered vaginal swab. The same type of swab will be used for the at-home self-swab and the clinician administered swab to allow for direct comparison of samples.

Participants recruited at sites may have a second clinic visit scheduled to collect the DDT and self-swab from the participant.

5.11. Questionnaires

A pre-sampling questionnaire will be sent to the participant upon enrolment before any samples have been taken. This questionnaire will assess the participants initial views on the DDT in advance of sampling. This questionnaire must be completed prior to the participant having any samples taken.

A second questionnaire (post-sampling questionnaire) will be sent to the participant following their clinic appointment(s) once all samples have been taken. This

questionnaire should only be completed once all other trial procedures have been performed. This questionnaire will compare the participants' experiences with the DDT versus the standard self-swab and clinician swab methods.

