Among the 60 participants who completed the study, the self-collected tampons demonstrated sensitivity and specificity of 66.67% (95% CI: 22.3%–95.7%) and 90.74% (95% CI: 79.7%–96.9%) when using TP Vial and 83.33% (95% CI: 51.6%–97.9%) and 85.42% (95% CI: 72.2%–93.9%) when using APTIMA for HPV detection, respectively. For BV detection, the tampons exhibited sensitivity and specificity of 100.0% (95% CI: 51.8%–99.7%) and 96.43% (95% CI: 87.7%–99.6%) (TP Vial) and 88.89% (95% CI: 22.3%–95.7%) and 98.04% (95% CI: 89.06%–100.0%) (APTIMA), respectively. For APTIMA Combo 2 (AC2) detection (for chlamydia and gonorrhoea), sensitivity and specificity were 100.00% (95% CI: 2.5%–100.0%) and 100.0% (95% CI: 93.9%–100.0%) (TP Vial) and 100.00% (95% CI: 2.5%–100.0%) and 98.31% (95% CI: 90.9%–100.0%) (APTIMA), respectively. Notably, 90% of participants expressed a preference for tampon self-collection over clinician-collected swabs.

Conclusion:

Self-collected tampons demonstrated comparable diagnostic accuracy to clinician-collected swabs for HPV and STI detection. The tampon self-collection method was well-accepted and preferred by participants, suggesting its potential as an alternative screening tool, particularly in low-resource settings. Further research with larger and more diverse populations is recommended to validate these findings and inform tampon-based self-collection programs for cervical cancer screening.

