2. OBJECTIVES AND OUTCOME MEASURES

Primary Objective

Objective	Outcome Measure	Timepoint(s) of evaluation
Evaluate the diagnostic accuracy of the Daye Diagnostic Tampon for detecting Chlamydia, Gonorrhoea, BV and HPV, specifically demonstrating a sensitivity of more than 70% for DDT.	Accuracy of the STI, BV and HPV testing using menstrual tampons compared to other specimen collection methods (clinician taken and self-swab) using the following assays: 
 - Hologic's APTIMA HPV (for HPV) - Hologic's APTIMA AC (for chlamydia and gonorrhoea) - Cepheid MPV assay (for BV) 	Within 4 weeks of the samples being received at the lab.

Secondary Objectives

Objective	Outcome Measure	Timepoint(s) of evaluation
Assess the usability of the DDT (via ASQ)	After scenario questionnaire scores	Post-sampling (once all samples are collected)
Explore participants views of the usability and acceptability of the DDT	Quantitative and qualitative feedback from pre- and post-sampling questionnaires and focus groups	Pre-sampling (baseline) and Post-sampling (once all samples are collected)
Assess whether the DDT is a preferred sampling	User preferences (self-report)	Pre-sampling (baseline) and Post-sampling (once

method for participants		all samples are collected)
Assess if the order of sample collection (self-swab vs DDT) impacts diagnostic accuracy	Diagnostic accuracy	Post sample analysis
Understand the health economic consequences of using the DDT for STI, BV and HPV testing	Willingness to pay for the DDT, comparison of time taken for DDT vs clinician swab	Post-sampling (once all samples are collected)
Explore stakeholder attitudes to tampons as a means of sample collection for microbial testing.	Qualitative feedback from stakeholder questionnaires	Ongoing throughout the trial once stakeholders have engaged with the tampon
Assess the occurrence of AEs/SAEs as a result of tampon sampling.	AE/SAE occurrence.	None expected, but any events will be collected and recorded on an ongoing basis as outlined in section 7.

Exploratory Objective

Objective	Outcome Measure	Timepoint(s) of evaluation
Explore the relationship between duration of wear and diagnostic accuracy.	Duration of DDT wear and diagnostic accuracy	Post sample analysis

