5.15. Early Discontinuation/Withdrawal of Participants

Each participant has the right to withdraw from the trial at any time. Participants leaving the trial before randomisation will be considered screen failures; participants leaving the trial after randomisation will be considered withdrawals.

Following participant withdrawal, no further trial assessments will be performed. The participant will be contacted by a member of the central team and a reason for withdrawal will be requested and documented.

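### The post-sampling questionnaire and the analysis set both depend on completed sampling, so participants who try but cannot complete the tampon drop out of ASQ usability and after-use preference

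*Protocol*

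**What the plan says.** Four parts of the protocol act together.

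- **Trigger (5.11).** The post-sampling questionnaire "will be sent to the participant following their clinic appointment(s) once all samples have been taken", and it "should only be completed once all other trial procedures have been performed". The outcome table in section 2 and both schedules in 5.1 give the same timing.
- **Content (section 2).** ASQ usability is measured only after sampling. Views on usability and acceptability, and preference, are measured at baseline and again after sampling. Of the baseline questionnaire, 5.11 says: "This questionnaire will assess the participants initial views on the DDT in advance of sampling".
- **Withdrawal (5.15).** "Following participant withdrawal, no further trial assessments will be performed". The central team does ask for and record a reason.
- **Analysis (8.4, 8.8).** Primary and secondary endpoints use complete pairs of DDT and clinician samples, and missing data are not replaced. Section 8.8 keeps participants who have swab results but lack a questionnaire. It does not address the reverse case.

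Section 8.1 states that no separate SAP is in use, so these rules are the full plan.

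**The concern.** One of the trial's aims is to judge how usable and acceptable the tampon is in its target population. Failing to insert it, removing it early or giving up is an adverse usability outcome in its own right. Under these rules, that same outcome decides whether the participant is asked about usability at all.

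The resulting ASQ scores, after-use preferences and change scores would describe people who completed sampling, while the conclusion is meant for everyone who might be offered the device. The loss happens at collection: no later analysis can recover answers that were never requested.

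**Working it through.** **Step 1. Follow a participant who attempts the DDT but yields no sample.**

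| Item | Collected or analysed? | Source |
|---|---|---|
| Baseline views and preference | Collected | 2, 5.11 |
| ASQ usability | Not triggered; no baseline value exists | 2, 5.11 |
| After-use views and preference | Not triggered | 2, 5.11 |
| Pre-to-post change | Cannot be formed without the second value | 8.2.2 |
| Withdrawal reason, if she withdraws | Requested | 5.15 |
| Any questionnaire she does return | Outside the stated population, as there is no DDT–clinician pair | 8.4 |

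The last row matters most. Even if a site sent her the questionnaire, 8.4 would leave it out.

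**Step 2. See who else the trigger removes.** It requires all samples, so it also removes people who miss the clinician swab or the self-swab. In the schedule for central and clinic-list recruitment (5.1.1) the clinician swab comes after the home samples, so a missed visit removes someone who may have used the DDT without difficulty. In the Italian in-person schedule (5.1.2) the clinician swab comes first, so what remains outstanding is the DDT or self-swab.

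**Step 3. Bound the effect on preference.** The protocol contains no figure to reproduce. Let *p* be preference among responders, *f* the share of enrolled participants without a post-sampling questionnaire, and *q* preference among that share.

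- Full-cohort preference = *p*(1 − *f*) + *q f*
- Overstatement = *p* − [*p*(1 − *f*) + *q f*] = *f*(*p* − *q*)

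Inputs:
- *p* = 90%, borrowed from the pilot in section 1.3: "Notably, 90% of participants expressed a preference for tampon self-collection over clinician-collected swabs". Using it for this trial is an assumption.
- N = 350 (section 8.3).
- *f* is not given. The inflation in 8.3 combines missing, lost and inconclusive samples with prevalence uncertainty. Assumed range: 2–20%.
- *q* is unknown, so it runs from 0 to 100%.

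| *f* | People | *q* = 0 | *q* = 100% |
|---|---|---|---|
| 2% | 7 | 0.90 × 0.98 = 88.2% | 88.2 + 2 = 90.2% |
| 5% | about 18 | 0.90 × 0.95 = 85.5% | 85.5 + 5 = 90.5% |
| 10% | 35 | 0.90 × 0.90 = 81.0% | 81.0 + 10 = 91.0% |
| 20% | 70 | 0.90 × 0.80 = 72.0% | 72.0 + 20 = 92.0% |

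At 10% loss the overstatement can reach 9 points and the understatement 1. At 20% the limits are 18 and 2.

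**Step 4. Check how far the asymmetry depends on *p*.** With *p* = 70% and *f* = 10%, the range is 0.70 × 0.90 = 63% to 63 + 10 = 73%, so up to 7 points over or 3 under. The sign depends only on whether *q* lies below *p*.

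No equivalent figure is offered for the ASQ, because the protocol gives neither its scale nor an expected score.

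**The case against.** The strongest reply is that 5.11 sets an order and not a condition. The questionnaire comes last so that participants can compare three methods, and nothing says that someone with a failed DDT is refused it. Section 8.8 expects missing samples and counts them, so such participants may remain in the trial. This reading is possible, but it does not rescue the plan: 8.4 would still exclude their answers.

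Other routes do exist. Focus groups cover usability and comfort, and joining one does not require a complete sample set. Withdrawal reasons and adverse events are recorded. None of these yields an ASQ score or an after-use preference, and the focus groups are optional and filled in order of response.

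A reader might infer stronger conclusions that the documents do not support:

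- *These participants give no preference data at all.* They do, at baseline.
- *Failing the tampon counts as withdrawal.* The protocol never says so. For those who stay in, the loss follows from the trigger and 8.4.
- *Preference must be biased towards the DDT.* People lost through a missed swab may favour the tampon, so *q* could exceed *p*.
- *This trial would report 90%.* That figure comes from a pilot of 60 completers and compares the tampon with clinician swabs only.

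It also stands that these endpoints are secondary and mainly descriptive.

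**Conclusion.** The concern holds, limited to ASQ usability, after-use preference and views, and pre-to-post change. As written, both the collection rule and the analysis set leave out participants who tried the DDT and could not complete it.

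For ASQ usability the expected bias favours the DDT. For preference the same direction is likely but not established. Its size cannot be found from the protocol. The ranges of 81–91% at 10% loss and 72–92% at 20% rest on an assumed loss rate, an assumed 90% among responders and no restriction on what non-responders prefer.

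The concern does not bear on the primary accuracy analysis. The plan should be changed because the selection depends on the outcome being measured, the lost answers cannot be recovered later, and the remedy is cheap.

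**What to change.** - **5.11, with the matching timepoints in 2 and 5.1.** Offer the post-sampling questionnaire at the end of each participant's sampling attempt, complete or not. Cover both the ePRO route and the Italian paper route. Add a response for each method, such as *tried but could not complete / did not use*, if the questionnaire does not already have one.
- **5.15.** Distinguish stopping sampling from withdrawing consent to further data collection, and let only the latter end questionnaire collection. The contact already made to ask the reason can be used to offer the questionnaire.
- **8.4.** Define a separate population for the questionnaire endpoints: all participants who attempted the DDT. Report how many could not complete it, and show completers as a secondary view. Without this change the added answers would remain outside the analysis.

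The cost is protocol wording, a changed ePRO trigger, an instruction for the paper route and possibly one response option. No extra visit is needed. The downside is some partly completed questionnaires and a possibly less favourable usability figure.

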5.12. Communication of Results

If the participant consents they will be informed of their test results directly via email. Participants will be advised that results are experimental and to contact their health provider if they are concerned.

UK

If the participant receives any positive results they will be offered the option of booking a call with a member of the trial team who will offer advice and support. The participant will be advised to contact their healthcare provider to request repeat testing via the standard pathways of care. Positive results for HPV do not replace the standard cervical screening service which all participants should continue to participate in. If the participant consents, their GP will also be informed of the results if any tests come back positive for a STI, BV or HPV.

Italy

In Italy the recruiting clinic will receive the results of the tests regardless of whether they are positive, negative or inconclusive and complete appropriate follow-up.

5.12.1. Process for discrepant results

In the event of discrepant results between sample types for the same participant the following process will be applied for communication of results to participants/GP/Dr:

1. Where possible the analysis on the discrepant sample will be repeated via re-extraction and re-running of the assay.
2. If, after repeat testing, 2 out of 3 samples are positive for an infection, the result will be reported as positive to the participant/GP/Dr.
3. If, after repeat testing, 1 out of the 3 samples are positive for an infection, the result will be reported as inconclusive to the participant/GP/Dr.

5.13. Qualitative Data Collection

5.13.1 Participant Focus Groups

Participants will have the option to take part in focus groups. This part of the trial will be optional. Participants will join a group discussion of 5–10 participants to explore in-depth their experiences with the DDT versus the other sampling methods.

15.3.1.1 Sampling

A list of participants who have consented for further contact for the focus group will be generated. Investigators will contact those in the sample list via email and/or phone until the required number of participants at each time point is reached. Inclusion will be given on a first come first served basis.

15.3.1.2 Focus Group Design

The focus groups will be semi-structured based on a topic guide. The focus groups will include 5–10 participants in each group and last up to 60 mins. Separate consent will be collected for participation in the focus group prior to the session starting. Focus groups will be conducted online using video conferencing software. All participants will be reminded before participation that they will be in an online group situation and accordingly, will be identifiable to the other participants. A trained facilitator who is part of the trial team will coordinate and guide the focus groups.

15.3.1.3 Focus Group Topics

A semi-structured topic guide will be used by the facilitator to initially engage participants in key topics and prompt focussed discussions. The guide will explore:

- Usability of the DDT
- Comfort using the DDT
- Acceptability and perceptions of using a tampon for sampling
- The DDT vs other common sampling methods

15.3.1.4 Focus Group Analysis

The transcript files will be downloaded from the video conferencing software and checked against the original recording for accuracy by a qualified member of the trial team who will generate an orthographic transcription for thematic analysis. The video will be deleted after checking is complete. Transcripts will be de-identified before coding to maintain confidentiality and privacy. The transcripts will be analysed using an inductive thematic analysis, an open coding approach in which themes and codes are generated from the data. This analysis follows a 6-step process outlined by Braun & Clarke, 2006¹¹ to include familiarising oneself with the data (step 1), generating codes (step 2), constructing themes (step 3), reviewing potential themes (step 4), defining and naming themes (step 5), and producing the report (step 6).

